11.1.8 C-SSRS

Data on Columbia-Suicide Severity Rating Scale (C-SSRS) will be summarized over time.

12.0 IDENTIFICATION AND SUMMARY OF PROTOCOL DEVIATIONS

Major protocol deviations from entry criteria and treatment compliance will be summarized as far as they can be extracted from numeric or coded study data.

13.0 DATA QUALITY ASSURANCE

Accurate and reliable data collection will be ensured by verification and cross check of the CRFs against the investigator's records by the study monitor (source document verification) and by the maintenance of a drug-dispensing log by the investigator. Collected data will be entered into a computer database and subject to electronic and manual quality assurance procedures.

14.0 REFERENCES

Not applicable.

15.0 APPENDICES

15.1 APPENDIX A - LIST OF TABLES, LISTINGS, AND FIGURES

List of Tables

| Number | Title |
|------------------|---|
| TABLE 14.1.1.1 | Disposition of Enrolled Patients (Overall Safety Population) |
| TABLE 14.1.1.2 | Disposition of Enrolled Patients (Full Exposure Safety Population) |
| TABLE 14.1.1.3 | Disposition of Enrolled Patients (Efficacy Population) |
| TABLE 14.1.2.1 | Demographics (Overall Safety Population) |
| TABLE 14.1.2.2 | Demographics (Full Exposure Safety Population) |
| TABLE 14.1.2.3 | Demographics (Efficacy Population) |
| TABLE 14.1.3.1 | Baseline Clinical Characteristics (Overall Safety Population) |
| TABLE 14.1.3.2 | Baseline Clinical Characteristics (Full Exposure Safety Population) |
| TABLE 14.1.3.3 | Baseline Clinical Characteristics (Efficacy Population) |
| TABLE 14.1.4.1 | Summary of Psychiatric History (Overall Safety Population) |
| TABLE 14.1.4.2 | Summary of Psychiatric History (Full Exposure Safety Population) |
| TABLE 14.1.4.3 | Summary of Psychiatric History (Efficacy Population) |
| TABLE 14.1.5.1.1 | Prior Medications (Overall Safety Population) |
| TABLE 14.1.5.1.2 | Prior Medications (Full Exposure Safety Population) |
| TABLE 14.1.5.1.3 | Prior Medications (Efficacy Population) |
| TABLE 14.1.5.2.1 | Concomitant Medications (Overall Safety Population) |
| TABLE 14.1.5.2.2 | Concomitant Medications (Full Exposure Safety Population) |
| TABLE 14.1.5.2.3 | Concomitant Medications (Efficacy Population) |
| TABLE 14.1.6.1 | Substance Abuse Treatment History (Overall Safety Population) |
| TABLE 14.1.6.2 | Substance Abuse Treatment History (Full Exposure Safety Population) |
| TABLE 14.1.6.3 | Substance Abuse Treatment History (Efficacy Population) |
| TABLE 14.2.1.1 | Summary of Urine Toxicology Results for Illicit Opioid Use Supported by Self-Reported Illicit Opioid Use over Time (Efficacy Population) |
| TABLE 14.2.1.2 | Summary of Urine Toxicology Results for Illicit Opioid Use Without Self-Reported Illicit Opioid Use over Time (Efficacy Population) |
| TABLE 14.2.2.1 | Summary of Mean Percentage of Urine Toxicology Results for Illicit Opioid Use Supported by Self-Reported Illicit Opioid Use (Efficacy Population) |
| TABLE 14.2.2.2 | Summary of Mean Percentage of Urine Toxicology Results for Illicit Opioid Use |

| | |
|-----------------|--|
| | Without Self-Reported Illicit Opioid Use (Efficacy Population) |
| TABLE 14.2.2.3 | Summary of Mean Percentage of Urine Toxicology Results for Illicit Opioids Use Supported by Self-Reported Illicit Opioid Use by Treatment Status at Baseline (New to Treatment [Yes/No]) |
| TABLE 14.2.2.4 | Summary of Mean Percentage of Urine Toxicology Results for Illicit Opioid Use Without Self-Reported Illicit Opioid Use by Treatment Status at Baseline (New to Treatment [Yes/No]) (Efficacy Population) |
| TABLE 14.2.3.1 | Summary of Self-Reported Illicit Opioid Use over Time (Efficacy Population) |
| TABLE 14.2.3.2 | Summary of Mean Percentage of Self-Reported Illicit Opioid Use (Efficacy Population) |
| TABLE 14.2.4.1 | Summary of Retention (%) in Treatment over Time (Efficacy Population) |
| TABLE 14.2.4.2 | Time to End of Retention in Treatment (Efficacy Population) |
| TABLE 14.2.5.1 | Summary of Retention (%) in Study over Time (Efficacy Population) |
| TABLE 14.2.5.2 | Time to End of Retention in Study (Efficacy Population) |
| TABLE 14.2.4.3 | Summary of Retention (%) in Treatment over Time by Treatment Status at Baseline (New to Treatment [Yes/No]) (Efficacy Population) |
| TABLE 14.2.4.4 | Time to End of Retention in Treatment by Treatment Status at Baseline (New to Treatment [Yes/No]) (Efficacy Population) |
| TABLE 14.2.6 | Summary of Clinical Opiate Withdrawal Scale (COWS) over Time (Efficacy Population) |
| TABLE 14.2.7 | Summary of Subjective Opiate Withdrawal Scale (SOWS) over Time (Efficacy Population) |
| TABLE 14.2.8 | Summary of Desire to Use VAS over Time (Efficacy Population) |
| TABLE 14.2.9 | Summary of Need to Use VAS over Time (Efficacy Population) |
| TABLE 14.2.10.1 | Summary of Urine Toxicology Results for Other Drugs of Abuse over Time (Efficacy Population) |
| TABLE 14.2.10.2 | Summary of Mean Percentage of Urine Toxicology Results for Other Drugs of Abuse (Efficacy Population) |
| TABLE 14.2.11 | Summary of Work Productivity and Activity Impairment Questionnaire General Health (WPAI-GH) by Item over Time (Efficacy Population) |
| TABLE 14.2.12 | Summary of EQ-5D-5L Health Questionnaire Data over Time (Efficacy Population) |
| TABLE 14.2.13 | Summary of Patient Satisfaction Scale Scores by Item over Time (Efficacy Population) |
| TABLE 14.3.1.1 | Summary of CAM2038 Exposure over Time (Overall Safety Population) |
| TABLE 14.3.1.2 | Summary of CAM2038 Exposure over Time (Full Exposure Safety Population) |
| TABLE 14.3.1.3 | Summary of CAM2038 Exposure by Dose and Number of Injections (Overall Safety Population) |
| TABLE 14.3.1.4 | Summary of CAM2038 Exposure by Dose and Number of Injections (Full Exposure Safety Population) |
| TABLE 14.3.2.1 | Summary of All Adverse Events by System Organ Class, Preferred Term, and Relationship (Overall Safety Population) |
| TABLE 14.3.2.2 | Summary of All Adverse Events by System Organ Class, Preferred Term, and Relationship (Full Exposure Safety Population) |
| TABLE 14.3.2.3 | Summary of All Injection-Related Adverse Events by System Organ Class, Preferred Term, and Relationship (Overall Safety Population) |
| TABLE 14.3.2.4 | Summary of All Injection-Related Adverse Events by System Organ Class, |

| | |
|------------------|--|
| | Preferred Term, and Relationship (Full Exposure Safety Population) |
| TABLE 14.3.2.5 | Summary of All Injection-Related Adverse Events by Preferred Term, Time to Onset and Duration (Overall Safety Population) |
| TABLE 14.3.2.6 | Summary of All Injection-Related Adverse Events by Preferred Term, Time to Onset and Duration (Full Exposure Safety Population) |
| TABLE 14.3.2.7 | Summary of All Non-Injection Related Adverse Events by System Organ Class, Preferred Term, and Relationship (Overall Safety Population) |
| TABLE 14.3.2.8 | Summary of All Non-Injection Related Adverse Events by System Organ Class, Preferred Term, and Relationship (Full Exposure Safety Population) |
| TABLE 14.3.3.1 | Summary of All Suspected to Be Drug-Related Adverse Events by System Organ Class and Preferred Term (Overall Safety Population) |
| TABLE 14.3.3.2 | Summary of All Suspected to Be Drug-Related Adverse Events by System Organ Class and Preferred Term (Full Exposure Safety Population) |
| TABLE 14.3.3.3 | Summary of All Injection Related Suspected to Be Drug-Related Adverse Events by System Organ Class and Preferred Term (Overall Safety Population) |
| TABLE 14.3.3.4 | Summary of All Injection Suspected to Be Drug-Related Adverse Events by System Organ Class and Preferred Term (Full Exposure Safety Population) |
| TABLE 14.3.3.5 | Summary of All Non-Injection Related Suspected to Be Drug-Related Adverse Events by System Organ Class and Preferred Term (Overall Safety Population) |
| TABLE 14.3.3.6 | Summary of All Non-Injection Suspected to Be Drug-Related Adverse Events by System Organ Class and Preferred Term (Full Exposure Safety Population) |
| TABLE 14.3.4.1 | Summary of All Adverse Events by System Organ Class, Preferred Term, and Severity (Overall Safety Population) |
| TABLE 14.3.4.2 | Summary of All Adverse Events by System Organ Class, Preferred Term, and Severity (Full Exposure Safety Population) |
| TABLE 14.3.4.3 | Summary of All Injection-Related Adverse Events by System Organ Class, Preferred Term, and Severity (Overall Safety Population) |
| TABLE 14.3.4.4 | Summary of All Injection-Related Adverse Events by System Organ Class, Preferred Term, and Severity (Full Exposure Safety Population) |
| TABLE 14.3.4.5 | Summary of All Non-Injection Related Adverse Events by System Organ Class, Preferred Term, and Severity (Overall Safety Population) |
| TABLE 14.3.4.6 | Summary of All Non-Injection Related Adverse Events by System Organ Class, Preferred Term, and Severity (Full Exposure Safety Population) |
| TABLE 14.3.5.1.1 | Summary of Most Common (at least 5%) Adverse Events by System Organ Class and Preferred Term (Overall Safety Population) |
| TABLE 14.3.5.1.2 | Summary (number of patients and number of events) of Most Common (at least 5%) Non-Serious Adverse Events by System Organ Class and Preferred Term (Overall Safety Population) |
| TABLE 14.3.5.1.3 | Summary (number of patients and number of events) of Serious Adverse Events by System Organ Class and Preferred Term (Overall Safety Population) |
| TABLE 14.3.5.2 | Summary of Most Common (at least 5%) Adverse Events by System Organ Class and Preferred Term (Full Exposure Safety Population) |
| TABLE 14.3.5.3 | Summary of Most Common (at least 5%) Injection-Related Adverse Events by System Organ Class and Preferred Term (Overall Safety Population) |
| TABLE 14.3.5.4 | Summary of Most Common Injection-Related (at least 5%) Adverse Events by System Organ Class and Preferred Term (Full Exposure Safety Population) |
| TABLE 14.3.5.5 | Summary of Most Common (at least 5%) Non-Injection Related Adverse Events |

| | |
|----------------|---|
| | by System Organ Class and Preferred Term (Overall Safety Population) |
| TABLE 14.3.5.6 | Summary of Most Common Non-Injection Related (at least 5%) Adverse Events by System Organ Class and Preferred Term (Full Exposure Safety Population) |
| TABLE 14.3.6.1 | Summary of All Serious Adverse Events by System Organ Class and Preferred Term (Overall Safety Population) |
| TABLE 14.3.6.2 | Summary of All Serious Adverse Events by System Organ Class and Preferred Term (Full Exposure Safety Population) |
| TABLE 14.3.6.3 | Summary of All Injection-Related Serious Adverse Events by System Organ Class and Preferred Term (Overall Safety Population) |
| TABLE 14.3.6.4 | Summary of All Injection-Related Serious Adverse Events by System Organ Class and Preferred Term (Full Exposure Safety Population) |
| TABLE 14.3.6.5 | Summary of All Non-Injection Related Serious Adverse Events by System Organ Class and Preferred Term (Overall Safety Population) |
| TABLE 14.3.6.6 | Summary of All Non-Injection Related Serious Adverse Events by System Organ Class and Preferred Term (Full Exposure Safety Population) |
| TABLE 14.3.7.1 | Summary of All Adverse Events That Lead to Treatment/Study Discontinuation by System Organ Class and Preferred Term (Overall Safety Population) |
| TABLE 14.3.7.2 | Summary of All Adverse Events That Lead to Treatment/Study Discontinuation by System Organ Class and Preferred Term (Full Exposure Safety Population) |
| TABLE 14.3.7.3 | Summary of All Injection Related Adverse Events That Lead to Treatment/Study Discontinuation by System Organ Class and Preferred Term (Overall Safety Population) |
| TABLE 14.3.7.4 | Summary of All Injection-Related Adverse Events That Lead to Treatment/Study Discontinuation by System Organ Class and Preferred Term (Full Exposure Safety Population) |
| TABLE 14.3.7.5 | Summary of All Non-Injection Related Adverse Events That Lead to Treatment/Study Discontinuation by System Organ Class and Preferred Term (Overall Safety Population) |
| TABLE 14.3.7.6 | Summary of All Non-Injection Related Adverse Events That Lead to Treatment/Study Discontinuation by System Organ Class and Preferred Term (Full Exposure Safety Population) |
| TABLE 14.3.8.1 | Summary of All Serious Adverse Events That Lead to Treatment/Study Discontinuation by System Organ Class and Preferred Term (Overall Safety Population) |
| TABLE 14.3.8.2 | Summary of All Serious Adverse Events That Lead to Treatment/Study Discontinuation by System Organ Class and Preferred Term (Full Exposure Safety Population) |
| TABLE 14.3.8.3 | Summary of All Injection Related Serious Adverse Events That Lead to Treatment/Study Discontinuation by System Organ Class and Preferred Term (Overall Safety Population) |
| TABLE 14.3.8.4 | Summary of All Injection Related Serious Adverse Events That Lead to Treatment/Study Discontinuation by System Organ Class and Preferred Term (Full Exposure Safety Population) |
| TABLE 14.3.8.5 | Summary of All Non-Injection Related Serious Adverse Events That Lead to Treatment/Study Discontinuation by System Organ Class and Preferred Term (Overall Safety Population) |
| TABLE 14.3.8.6 | Summary of All Non-Injection Related Serious Adverse Events That Lead to |

| | |
|-----------------|--|
| | Treatment/Study Discontinuation by System Organ Class and Preferred Term (Full Exposure Safety Population) |
| TABLE 14.3.9.1 | Summary of All Deaths and Hospitalizations (Overall Safety Population) |
| TABLE 14.3.9.2 | Summary of All Deaths and Hospitalizations (Full Exposure Safety Population) |
| TABLE 14.3.9.3 | Summary of All Injection-Related Deaths and Hospitalizations (Overall Safety Population) |
| TABLE 14.3.9.4 | Summary of All Injection-Related Deaths and Hospitalizations (Full Exposure Safety Population) |
| TABLE 14.3.9.5 | Summary of All Non-Injection Related Deaths and Hospitalizations (Overall Safety Population) |
| TABLE 14.3.9.6 | Summary of All Non-Injection Related Deaths and Hospitalizations (Full Exposure Safety Population) |
| TABLE 14.3.10.1 | Summary of Columbia-Suicide Severity Ratings over Time (Overall Safety Population) |
| TABLE 14.3.10.2 | Summary of Columbia-Suicide Severity Ratings over Time (Full Exposure Safety Population) |
| TABLE 14.3.11.1 | Summary of Clinical Hematology Data over Time (Overall Safety Population) |
| TABLE 14.3.11.2 | Summary of Clinical Hematology Data over Time (Full Exposure Safety Population) |
| TABLE 14.3.12.1 | Shift from Baseline in Laboratory Tests: Hematology (Overall Safety Population) |
| TABLE 14.3.12.2 | Shift from Baseline in Laboratory Tests: Hematology (Full Exposure Safety Population) |
| TABLE 14.3.13.1 | Summary of Clinical Chemistry Data (Overall Safety Population) |
| TABLE 14.3.13.2 | Summary of Clinical Chemistry Data (Full Exposure Safety Population) |
| TABLE 14.3.14.1 | Shift from Baseline in Laboratory Tests: Chemistry (Overall Safety Population) |
| TABLE 14.3.14.2 | Shift from Baseline in Laboratory Tests: Chemistry (Full Exposure Safety Population) |
| TABLE 14.3.15.1 | Summary of Clinical Coagulation Profile Data (Overall Safety Population) |
| TABLE 14.3.15.2 | Summary of Clinical Coagulation Profile Data (Full Exposure Safety Population) |
| TABLE 14.3.16.1 | Shift from Baseline in Laboratory Tests: Coagulation Profile (Overall Safety Population) |
| TABLE 14.3.16.2 | Shift from Baseline in Laboratory Tests: Coagulation Profile (Full Exposure Safety Population) |
| TABLE 14.3.17.1 | Summary of Vital Signs over Time (Overall Safety Population) |
| TABLE 14.3.17.2 | Summary of Vital Signs over Time (Full Exposure Safety Population) |
| TABLE 14.3.18.1 | Summary of 12-Lead ECG Results (Overall Safety Population) |
| TABLE 14.3.18.2 | Summary of 12-Lead ECG Results (Full Exposure Safety Population) |
| TABLE 14.3.19.1 | Summary of 12-Lead ECG Individual Parameters (Overall Safety Population) |
| TABLE 14.3.19.2 | Summary of 12-Lead ECG Individual Parameters (Full Exposure Safety Population) |

List of Listings

| Number | Title |
|------------------|-------------------------------------|
| LISTING 16.2.1.1 | Patient Meeting Inclusion Criteria |
| LISTING 16.2.1.2 | Patients Meeting Exclusion Criteria |
| LISTING 16.2.2 | Protocol Deviations |

| | |
|------------------|--|
| LISTING 16.2.3 | Patient Disposition |
| LISTING 16.2.4.1 | Demographics |
| LISTING 16.2.4.2 | Psychosocial History |
| LISTING 16.2.4.3 | Medical History |
| LISTING 16.2.4.4 | Substance Abuse History and Treatment |
| LISTING 16.2.5.1 | CAM2038 Injection |
| LISTING 16.2.5.2 | Injection Site Examination/ Treatment Compliance |
| LISTING 16.2.6.1 | COWS, SOWS |
| LISTING 16.2.6.2 | Need to Use and Desire to Use VAS |
| LISTING 16.2.6.3 | Urine Toxicology Results for Illicit Opioids |
| LISTING 16.2.6.4 | Self-Reported Illicit Opioid Use |
| LISTING 16.2.6.5 | Urine Toxicology Results for Other Drugs of Abuse |
| LISTING 16.2.6.6 | Work Productivity and Activity Impairment Questionnaire General Health (WPAI-GH) |
| LISTING 16.2.6.7 | EQ-5D-5L Health Questionnaire |
| LISTING 16.2.6.8 | Patient Satisfaction Scale |
| LISTING 16.2.6.9 | Psychosocial Counseling |
| LISTING 16.2.7.1 | Adverse Events |
| LISTING 16.2.7.2 | Serious Adverse Events |
| LISTING 16.2.7.3 | Adverse Events That Lead to Discontinuation from Treatment/Study |
| LISTING 16.2.7.4 | Adverse Events That Have Death as the Outcome |
| LISTING 16.2.7.5 | Death Reports |
| LISTING 16.2.7.6 | Prior and Concomitant Medications/Procedures |
| LISTING 16.2.8.1 | Lab Test Samples |
| LISTING 16.2.8.2 | Clinical Hematology |
| LISTING 16.2.8.3 | Clinical Chemistry |
| LISTING 16.2.8.4 | Clinical Coagulation Profile |
| LISTING 16.2.8.5 | Urinalysis |
| LISTING 16.2.8.6 | Serology |
| LISTING 16.2.8.7 | Pregnancy Test |
| LISTING 16.2.8.8 | Pregnancies |
| LISTING 16.2.9 | C-SSRS |
| LISTING 16.2.10 | Physical Examination |
| LISTING 16.2.11 | Vital Signs |
| LISTING 16.2.12 | 12-Lead ECG |
| LISTING 16.2.13 | Patient Visits |

List of Figures

| | |
|---------------|---|
| FIGURE 14.2.1 | Kaplan-Meier Plot of Time to Treatment Discontinuation (retention in treatment) (Efficacy Population) |
| FIGURE 14.2.2 | Kaplan-Meier Plot of Time to Study Discontinuation (retention in study) (Efficacy Population) |
| FIGURE 14.2.3 | Urine Toxicology Results for Illicit Opioid Use Supported by Self-Reported Illicit Opioid Use by Time (Efficacy Population) |
| FIGURE 14.2.4 | Urine Toxicology Results for Illicit Opioid Use Without Self-Reported Illicit Opioid Use by Time (Efficacy Population) |

15.2 APPENDIX B - IMPUTATION ALGORITHM FOR PARTIAL AND MISSING DATES

This section describes missing date imputation methods.

For Adverse Events

If onset date is completely missing, onset date is set to the date of first study dose date.

If (year is present and month and day are missing) or (year and day are present and month is missing):

- If year = year of first dosing, then set month and day to month and day of first dosing
- If year < year of first dosing, then set month and day to December 31.
- If year > year of first dosing, then set month and day to January 1.

If month and year are present and day is missing:

- If year=year of first dosing and
 - If month = month of first dosing then set day to day of first dose
 - If month < month of first dose then set day to last day of month
 - If month > month of first dose then set day to first day of month
- If year < year of first dosing then set day to last day of month
- If year > year of dosing then set day to first day of month

For all other cases, set onset date to date of first dosing.

For Concomitant Medications

Start Date: If start date is completely missing and end date is not prior to first dosing, then the medication will be classified as concomitant. If start date is completely missing and end date is prior to first dosing, then the medication will be classified as prior.

If (year is present and month and day are missing) or (year and day are present and month is missing) then set month and day to January 1. If year and month are present and day is missing then set day to first day of month.

End Date: If end date is completely missing then the medication will be classified as concomitant.

If (year is present and month and day are missing) or (year and day are present and month is missing) then set month and day to December 31. If year and month are present and day is missing then set day to last day of the month.

Note: that if both start and end dates are missing then the medication will be classified as concomitant.

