9.4.1.1. Adverse Event Reporting

All AEs (except for withdrawal symptoms, see below) must be entered on the AE CRF, regardless of causality or severity. AEs include new AEs, worsening baseline conditions, clinically significant laboratory findings, disease-related signs and symptoms that were not present at baseline, and any events or findings that the Investigator feels are clinically significant. Withdrawal symptoms will be captured via specified assessments and should not be recorded as AEs.

Disease-related signs and symptoms that are present at baseline should not be recorded as AEs unless they worsen in severity or increase in frequency.

Information collected concerning AEs will include the following:

- Name of the event
- Onset date
- Resolution date
- Severity (i.e., mild, moderate, or severe)
- Relationship to study drug
- Action and outcome
- Seriousness of event

Definition of MILD, MODERATE, SEVERE AE:

- Mild- An AE that requires minimal treatment and does not interfere with daily living.
- Moderate- An AE that requires therapeutic intervention and interferes with daily living.
- Severe- An AE that requires intensive therapeutic intervention, significant, etc.

All AEs will be documented and followed from the time the subject has signed the ICF until 14 days after the Follow-up Visit (or 30 days after early termination). Serious AEs and AEs that have been designated as possibly related to study drug will be followed until resolution or stabilization.

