11.1.2 ADVERSE EVENTS

Each AE and serious adverse event (SAE) term recorded on the CRFs by primary system organ class (SOC) and will be mapped to a preferred term (PT) using the MedDRA dictionary. The Investigator will assess AE severity and relationship to the study treatment.

A treatment-emergent adverse event (TEAE) is defined as any AE with an onset date on or after the date of the first study treatment, or any ongoing event started on the date of the first dose that worsens in severity. Only AEs with an onset date prior to the date of the last dose + 30 days will be tabulated in summary tables. For the purpose of calculating treatment emergence and inclusion in summary tables, incomplete onset dates will be imputed as detailed in Appendix B.

AEs will be summarized by the number and percent of patients in each primary SOC and PT. Patients will be counted only once for each primary SOC and each PT. Summary tables of AEs by primary SOC, PT and intensity will be provided. If a patient has more than one AE coded to the same PT, the patient will be counted only once for that PT by using the event with the highest intensity. Similarly, if a patient has more than one AE within a primary SOC category, the patient will be counted only once in that SOC category by using the event with the highest intensity. AEs by primary SOC, PT and relationship to study drug will be provided as well. If a patient has more than one AE coded to the same PT, the patient will be counted only once for that PT by using the most related event. Similarly, if a patient has more than one AE within a primary SOC category, the patient will be counted only once in that primary SOC category by using the most related event. In addition, SAEs by primary SOC and PT will be provided. Deaths and SAEs will be summarized similarly to AEs. All AE tables will also include the total number of events, counting multiple events per patient.

Injection-related AEs, other (non-injection related) AEs as well as all AEs will be presented. Summaries of these AE subsets will be presented for the following categories:

- Study drug-related
- Intensity
- Serious
- AEs which led to treatment/study discontinuation
- SAEs which led to treatment/study discontinuation
- AEs occurring in 5% or greater of patients (by preferred term)

In the AE summary, the SOCs and the PTs within each SOC will appear in descending order of frequency.

Frequencies of deaths and hospitalizations will also be summarized.

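### SAP Appendix B sets certain missing or partial AE onset dates to the first dosing day without checking the resolution date, so an AE known to have resolved in Screening can be classed as treatment-emergent.

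*SAP*

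**What the plan says.** SAP 11.1.2 defines treatment emergence by onset: "A treatment-emergent adverse event (TEAE) is defined as any AE with an onset date on or after the date of the first study treatment". For deciding emergence, and inclusion in the summary tables, "incomplete onset dates will be imputed as detailed in Appendix B".

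The AE part of Appendix B assigns the first dosing day in these cases:

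- Onset completely missing: "If onset date is completely missing, onset date is set to the date of first study dose date".
- Month missing, year known: "If year = year of first dosing, then set month and day to month and day of first dosing".
- Only the day missing, in the year of first dosing: "If month = month of first dosing then set day to day of first dose".
- Anything not otherwise covered: "For all other cases, set onset date to date of first dosing".

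A partial onset in an earlier year or month goes to the last day of that period, which is before first dose.

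Protocol 9.4.1.1 starts AE recording at consent: "All AEs will be documented and followed from the time the subject has signed the ICF". The same section lists the resolution date among the items collected. Protocol 7.1.1 places Screening one to three weeks before Day 1, and Table 3 schedules AE recording at Screening.

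The medication rules in Appendix B do use the end date: "If start date is completely missing and end date is prior to first dosing, then the medication will be classified as prior".

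**The concern.** Setting an uncertain onset to the first dosing day is a sound cautious convention when the event might have begun on treatment. It has no justification when the record shows that the event was over before the first injection, because nothing about treatment emergence is then uncertain. The AE rules make no exception for that case. An event confined to Screening is given an onset later than its own end and meets the TEAE definition.

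The primary objective is safety and tolerability, and AE incidence is one of the main safety results. What is at stake is the correct split between events before and after treatment began. The field needed to make that split, the resolution date, is already collected.

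**Working it through.** The plan states no figure on this point, so there is none to reproduce. The check applies the rules as written.

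**One case (assumed dates).** First dose is on 25 March. An AE is recorded at Screening with onset in March of the same year, day unknown, and resolution on 18 March. The month equals the month of first dosing, so onset becomes 25 March, seven days after the event ended. Since 25 March is on or after first treatment, the AE is a TEAE.

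**All cases in a three-week Screening window.** Take true onsets from 1 to 21 days before first dose, with resolution on or after onset but before first dose. If onsets up to k days before first dose are included, the number of onset/end pairs is 1 + 2 + ... + k = k(k+1)/2. For k = 21 this is 21 × 22 / 2 = 231. None of these events is truly treatment-emergent. The table gives the number classed as TEAEs for three assumed first-dose dates in 2016.

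| What is recorded for onset | First dose 25 March | 5 March | 10 January |
|---|---|---|---|
| Complete date | 0 | 0 | 0 |
| Completely missing | 231 | 231 | 231 |
| Year only | 231 | 231 | 45 |
| Month and year | 231 | 10 | 45 |

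The smaller entries arise as follows:

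- First dose 5 March, month and year known: only onsets on 1 to 4 March share the month of first dosing, so k = 4 and 4 × 5 / 2 = 10. The other 221 pairs (231 − 10) go to the last day of February and are correctly not TEAEs.
- First dose 10 January: only onsets on 1 to 9 January share the month and year of first dosing, so k = 9 and 9 × 10 / 2 = 45. The other 186 pairs (231 − 45) go to 31 December and are correctly not TEAEs.

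With an end-date check added, every entry becomes 0 of 231. AEs whose end date is unknown, or is on or after first dose, keep their classification.

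These are counts over an even grid of possible dates. They show when the rule fails, not how many events to expect.

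**Scale of one event.** Suppose the AE tables are limited to TEAEs, and one patient is counted wrongly for a term not also reported after dosing. That adds 1/228 = 0.4 percentage points if all 228 planned patients are dosed, or 1/100 = 1 point in a Full Exposure Safety Population of 100.

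**The case against.** The strongest case on the other side accepts the gap in wording and disputes its consequences. Most of that stands.

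- **Causality.** A reader might infer that pre-treatment events become attributed to CAM2038. The documents do not support this. Under SAP 11.1.2 the Investigator assesses relationship to study drug. Treatment-emergent is a timing label, and the imputation leaves causality alone.
- **Impossible records in the output.** A reader might expect onsets after resolution, or negative durations, in the report. SAP 6.0 says listings present the data collected on the CRF, and 11.1.2 confines imputation to treatment emergence and table inclusion. The only planned duration tables (14.3.2.5 and 14.3.2.6) cover injection-related AEs, where an event that ended before the first injection should not appear.
- **Inflated tables.** A reader might infer that every AE table is inflated. The titles in Appendix A refer to all adverse events and never to TEAEs, and the only cut-off stated for tabulation is 30 days after last dose. If the tables are not limited to TEAEs, a Screening AE is tabulated whatever its onset, and the imputation changes nothing in them. Patients are also counted once per term and class, so a patient count rises only if the patient has no other counted event there.
- **Rarity.** The fault needs a Screening AE, a recorded end before dosing, and an onset that is missing or partial in the first-dose month or year. AEs are elicited at each visit and the data are checked, so such records may be few or absent.
- **The medication comparison.** SAP 9.0 defines prior medication by its stop date, so that rule has to use the end date, whereas TEAEs are defined by onset. The contrast therefore does not prove an inconsistency. It shows only that the appendix consults an end date where that settles the matter.

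None of this removes the misclassification. No other section of either document excludes an AE that resolved before first dose.

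**Conclusion.** The point holds as a minor error in a stated rule. For an onset that is completely missing, known only to the year of first dosing, or known only to its month and year, Appendix B assigns the first dosing day even when the recorded resolution precedes it. SAP 11.1.2 then makes that AE treatment-emergent.

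The error runs one way: it can over-count TEAEs and cannot hide one. It is probably small, given a pre-dose window of about three weeks. Its size cannot be estimated, because the documents give no count of AEs with incomplete onset dates, and the number affected could be zero. The conclusion rests on the rules being programmed as written and on at least some Screening AEs having a known end date but an incomplete onset.

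It does not support a claim that TEAE counts are the sole or primary safety output. SAP 11.0 bases the safety evaluation on AEs together with vital signs, ECG, laboratory results and injection site examinations.

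**What to change.** Add at the top of the AE algorithm in Appendix B: if the recorded end date, or the parts of it that are known, establishes that the AE resolved before first dosing, the AE is not treatment-emergent and its imputed onset is no later than its end date. If the end date is missing, or does not establish this, apply the existing rules.

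The reference to known parts is needed because Appendix B has no rule for partial AE end dates. An end date known only to a month before the month of first dosing settles the question; one known only to the month of first dosing does not. The cap also covers partial onsets in an earlier month, where the last day of that month can fall after a recorded end date.

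The cost is one sentence and a small programming change. The downside is also small: an erroneous end date could remove a true TEAE, so every record that the check changes should be queried with the site. SAP 3.0 allows revision before database lock. If the database is already locked, look for affected records and describe their handling in the study report.
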